4.3.2 Study Drug Administration

Induction – Alvocidib and 7+3

- *Days 1, 2, 3:* Alvocidib at a starting dose of 20 mg/m² as a 30-minute (±10 minutes) IV bolus followed by 30 mg/m² administered as a 4-hour (±15 minutes) IV infusion (this is the starting dose for Cohort 1; see [Table 3](#) for assigned alvocidib doses per treatment cohort)
- *Day 4:* Drug-free day
- *Days 5, 6, 7: (7+3)* Daunorubicin 60 mg/m² via IV bolus of up to 15 minutes' (±5 minutes) duration each day followed immediately by;
- *Days 5, 6, 7, 8, 9, 10, 11:* Cytarabine 100 mg/m²/day via continuous 24-hour IV infusion (±2 hours for infusion duration each day)

Reinduction – Alvocidib and 5+2

Patients **with** evidence of residual leukemia defined as >5% bone marrow blasts plus >10% cellularity, based on the Day 14 (±3 days) bone marrow will be eligible to start a second induction cycle (ie, Reinduction) with alvocidib plus 5+2. The second induction cycle with alvocidib plus 5+2 will be allowed per investigator discretion.

- *Days 1, 2, 3:* Alvocidib at same dosage as during Induction
- *Day 4:* Drug-free day
- *Days 5, 6: (5+2)* Daunorubicin 45 mg/m²/day via IV bolus of up to 15 minutes' (±5 minutes) duration each day followed immediately by;
- *Days 5, 6, 7, 8, 9:* Cytarabine 100 mg/m²/day via continuous IV infusion (±2 hours for infusion duration each day)

Consolidation – HiDAC

Consolidation therapy will consist of high-dose cytarabine (HiDAC) which may be initiated at the time of hematologic recovery or within 90 days of recovery. Consolidation therapy may start before complete hematologic recovery after discussion with the Medical Monitor. It is not anticipated that all patients will undergo Consolidation therapy.

- *Days 1, 3, 5:* HiDAC 3 gm/m² IV every 12 hours (1.5 gm/m² in patients aged 60 to 65 years) (ie, a total of 6 doses over the 3-day regimen); lower starting dose may be permitted at the discretion of the Investigator and after discussion with the Medical Monitor

Patients who plan to receive chemotherapy-based consolidation should get a minimum of two cycles of Consolidation up to a maximum of four cycles. Patients proceeding to stem cell transplant for Consolidation should get one cycle of Consolidation, if possible, to ensure disease stability while transplant plans are being made.

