Open label, multicenter, 3+3 cohort dose escalation of alvocidib for induction therapy combined with 7+3 cytarabine and daunorubicin, followed by optional reinduction with alvocidib combined with 5+2 cytarabine and daunorubicin and/or up to 4 cycles of consolidation therapy with high-dose cytarabine (HiDAC)

Study Populations:

Patients with newly diagnosed, previously untreated AML excluding acute promyelocytic leukemia or core-binding factor AML

Induction Therapy (alvocidib with 7+3):

- Alvocidib on Days 1-3
 - 20-mg/m² IV bolus followed by 30-mg/m² IV infusion over 4 hours, or
 - 30-mg/m² IV bolus followed by 40-mg/m² IV infusion over 4 hours, or
 - 30-mg/m² IV bolus followed by 50-mg/m² IV infusion over 4 hours, or
 - 30-mg/m² IV bolus followed by 60-mg/m² IV infusion over 4 hours
- Cytarabine 100 mg/m²/day continuous IV infusion on Days 5-11
- Daunorubicin 60-mg/m² IV bolus on Days 5-7

Optional Reinduction Therapy (alvocidib with 5+2):

- Alvocidib on Days 1-3 at the same dose used for induction
- Cytarabine 100 mg/m²/day continuous IV infusion on Days 5-9
- Daunorubicin 60-mg/m² IV bolus on Days 5-6

Optional Consolidation Therapy (HiDAC up to 4 cycles):

- Cytarabine 3 g/m² IV q12h on Days 1, 3 and 5 for a total of 6 doses
- A reduced dose of 1.5 g/m² IV q12h was permitted for patients ≥60 years old

Sample Size:

A sufficient number of patients to complete a standard 3+3 cohort dose escalation for up to 4 dose levels plus up to 20 additional patients enrolled at the maximum tolerated dose (MTD) of alvocidib

Analysis Populations:

Intent-to-treat (primary for efficacy), safety, per-protocol

Response Assessments:

Local review of bone marrow and blood test results by the investigator at the study center where patient is enrolled to classify response to treatment following to European LeukemiaNet (ELN) criteria¹

Missing Values:

Missing values will not be replaced by imputed values. Patients who do not supply bone marrow for response assessment are counted among those not achieving remission. Missing time-to-event endpoints will be censored using standard rules detailed below.

Interim Analysis:

No interim analyses. Ongoing review of clinical data performed as required for dose escalation/de-escalation decisions

Efficacy Endpoints:

CR rate (primary endpoint), combined CR rate, combined remission rate, stem cell transplant rate, overall survival, progression-free survival, relapse-free survival, CR duration

Safety Endpoints:

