Cycle 1: period of time from the first dose of study drug until the start of study drug in cycle 2 or the start of alternative AML therapy other than supportive measures such as blood product transfusions (hence a patient whose first response assessment in cycle 1 is a CRi is considered to have achieved CR if neutrophils and platelets recover prior to initiation of cycle 2 or alternative AML therapy)

Combined CR Rate: percentage of patients who achieve a combined CR following treatment with alvocidib

Combined Remission Rate: percentage of patients who achieve a combined remission following treatment with alvocidib

CR Rate: percentage of patients who achieve a CR following treatment with alvocidib (see section 7.8.1)

Dose-Limiting Toxicity: Refer to the study protocol for the specific conditions and events that qualify as a dose-limiting toxicity (DLT)

Intent-to-Treat Population: all patients enrolled in the study regardless of whether they actually received study drug and regardless of whether evidence is found indicating they failed to meet study inclusion/exclusion criteria or had other protocol violations (see section 7.1)

Minimal Residual Disease Negative: Absence of gene fusion transcripts using standardized techniques such as multiparametric flow cytometry or next generation sequencing

Neutrophil Recovery: Absolute neutrophil count ≥1x10⁹/L following the administration of study drug

Per-Protocol Population: The subset of safety patients who either (a) have at least one response assessment on study, or (b) die prior to their first scheduled response assessment; however, patients are excluded from the per-protocol population if they have an important protocol deviation, such as when evidence is found indicating they failed to meet any study inclusion/exclusion criterion (see section 7.1)

Platelet Recovery: Platelet count ≥100x10⁹/L following the administration of study drug

Prestudy: Occurrence prior to the first administration of study drug

Safety Population: The subset of intent-to-treat patients who received at least one dose or partial dose of study drug (see section 7.1)

Shift Table: two-way frequency table pairing baseline value with the most extreme post-baseline result

Study Drug: alvocidib, Ara-C (cytarabine) and mitoxantrone

Treatment Failure: failing to achieve a CR, CRi or PR following induction therapy (see section 7.8.2)

4. Introduction

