4.2. Statistical Objectives

The statistical objectives are threefold:

- 1. To define a maximum tolerated dose of alvocidib administered with cytarabine and daunorubicin in newly diagnosed AML patients
- 2. To describe the safety and efficacy of alvocidib administered with cytarabine and daunorubicin in newly diagnosed AML patients

3. To model the relationship between baseline MCL-1 dependence and response to treatment with alvocidib administered with cytarabine and daunorubicin

5. Sample Size

The sample size for this study is not predetermined. The number of patients enrolled depends on the occurrence and pattern of DLTs.

6. Treatment Assignment

Cohorts of 3 patients are assigned a dose of alvocidib according to standard 3+3 dose escalation/de-escalation rules. All patients receive the same, standard doses of cytarabine and daunorubicin.

7. Statistical Methods

Analyses will be performed using SAS statistical software. Default estimation methods in version 9.4 of SAS are always used unless an alternative is specified below. Data summaries will include the mean, standard deviation, median, minimum and maximum values for continuous data; the median, 25th and 75th percentiles, minimum and maximum values for time-to-event endpoints; and the number and percentage of patients in each category for categorical data. Pointwise 95% confidence intervals (CI) will also be estimated for the mean (continuous data), median (time-to-event endpoints) or percentage of patients (categorical data).

In general, data values will be obtained directly from the clinical database (e.g., birth date, treatment dates, AML relapse date and death date). Derivations for certain values not collected explicitly in the database are explained in relevant sections below (e.g., age and treatment failure date, sections 7.6 and 7.8.2, respectively). In some instances, it is beyond the scope of this SAP to explain schemes for patient classifications and data derivations (e.g., classifying patients in cytogenetic risk group according to published criteria). These details will be expounded in the clinical study report.

Durations of time expressed in months (e.g., times-to-event endpoints) will be reported in proportional "months" according to the formula

months =
$$\frac{12}{365.25} \times \text{days}$$

Baseline value of a characteristic is defined as the last measured value prior to the first dose of study drug.

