7.9. Biomarker

The biomarker in this study is MCL-1 dependence measured by mitochondrial sensitivity to NOXA BH3 peptides. Relevant data supporting analyses of MCL-1 dependence will be listed by patient within alvocidib dose level. Summary of baseline biomarker values will include descriptive statistics appropriate for continuous variables (see section 7.6). An LR model will be fit to examine the relationship between baseline MCL-1 dependence and the independent binary variable CR for newly diagnosed AML patients receiving ACM. In addition, area under the curve (AUC) will be calculated (by treatment

arm) for the trapezoidal receiver operating characteristic (ROC) curve. This value will quantify the ability of MCL-1 dependence to predict CR.¹¹ Ninety-five percent Cls will be calculated by assuming estimated AUC follows a normal distribution.

$$\widehat{AUC} \pm z_{1-\alpha/2} SE_{AUC}$$

where the standard error SE_{AUC} is calculated by the jackknife method.¹² Similar analyses will be conducted for combined CR and combined remission.

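### The SAP's definition of study drug lists mitoxantrone, which nobody is scheduled to receive, and omits daunorubicin, so the exposure summary read literally leaves out one of the three induction agents

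*SAP*

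**What the plan says.** SAP Section 3 sets the term: "Study Drug: alvocidib, Ara-C (cytarabine) and mitoxantrone".

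Elsewhere the SAP describes a different regimen:

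- The synopsis has "alvocidib for induction therapy combined with 7+3 cytarabine and daunorubicin".
- The first statistical objective in Section 4.2 is "To define a maximum tolerated dose of alvocidib administered with cytarabine and daunorubicin in newly diagnosed AML patients". The second and third objectives name the same two partner drugs.
- Section 6 states "All patients receive the same, standard doses of cytarabine and daunorubicin".

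Protocol 4.3.2 agrees with these. Induction on Days 5 to 7 has "Daunorubicin 60 mg/m² via IV bolus", and Reinduction on Days 5 and 6 has "Daunorubicin 45 mg/m²/day via IV bolus". Mitoxantrone is in neither schedule.

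SAP 7.9 describes the biomarker model as relating baseline MCL-1 dependence to "the independent binary variable CR for newly diagnosed AML patients receiving ACM". The protocol's abbreviation list assigns ACM to the mitoxantrone regimen and ACD to alvocidib plus 7+3.

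The defined term is used in SAP 7.7 (exposure) and in SAP 7.10.2 and Table 3 (adverse events leading to a change in study drug). None of these lists the agents.

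**The concern.** A definition governs every output that uses its term. This one names a drug outside the trial and leaves out one that every patient is scheduled to receive. The primary objective is the safety and tolerability of alvocidib followed by 7+3. Exposure and dose-change tables are supporting information for it: they tell the reader how much of the regimen was delivered and why doses changed.

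Daunorubicin is a poor agent to lose from those tables. Protocol 4.4.4 rules out reductions of alvocidib and cytarabine in Induction and Reinduction. It requires daunorubicin cuts of 25% or 50% by direct bilirubin, and omission from later cycles above a lifetime equivalent of 460 mg/m² or with LVEF below 45%.

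The text looks carried over from another plan. The SAP abbreviations still list CM for cytarabine with mitoxantrone, and the appendix footers cite TPI-ALV-201, while the SAP Introduction says the plan covers TPI-ALV-101.

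**Working it through.** The plan gives no figure on this point to reproduce. The check compares the texts and adds up planned doses.

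**1. Agents in each source**

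| Agent | SAP Section 3 | SAP synopsis, 4.2 and 6 | Protocol 4.3.2 |
|---|---|---|---|
| Alvocidib | yes | yes | yes |
| Cytarabine | yes | yes | yes |
| Daunorubicin | no | yes | yes |
| Mitoxantrone | yes | no | no |

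**2. Outputs that rest on the term**

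- Exposure: one SAP Table 3 title, planned for three populations, so 3 outputs.
- TEAEs leading to delay, reduction or discontinuation: three titles, each for the safety population, so 3 outputs. They are also 3 of the 10 rows in the high-level summary in SAP 7.10.2.

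The exposure effect follows directly from the definition. The effect on the other three titles also depends on whether the eCRF records action taken for each agent or once for the regimen.

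**3. Planned daunorubicin outside the definition (protocol 4.3.2 doses)**

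- Induction: 3 × 60 = 180 mg/m².
- Reinduction: 2 × 45 = 90 mg/m².
- Both: 180 + 90 = 270 mg/m².

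The SAP synopsis gives a different Reinduction dose, "Daunorubicin 60-mg/m² IV bolus on Days 5-6". That is a separate discrepancy, which correcting the definition does not resolve, so the protocol dose is used here.

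**4. Size of a bilirubin-driven cut in Induction**

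- One dose: 0.25 × 60 = 15 mg/m², or 0.50 × 60 = 30 mg/m².
- All three doses: 0.25 × 180 = 45 mg/m², or 0.50 × 180 = 90 mg/m².

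The range is therefore 15 to 90 mg/m², from one dose cut by 25% to all three cut by 50%. The documents give no rate of such cuts. A cut also reaches a TEAE table only if the laboratory change was recorded as an adverse event, which under protocol 8.4 needs clinical sequelae or a therapeutic intervention.

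**5. What does not move**

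- Safety population, baseline and start of the TEAE window: fixed by the first dose, which is alvocidib on Day 1.
- End of the TEAE window: fixed by the last dose. As scheduled, that is cytarabine (Day 11 against Day 7 for daunorubicin in Induction, Day 9 against Day 6 in Reinduction), or HiDAC later.
- DLTs and MTD: SAP Section 3 refers to the protocol for what counts as a DLT.
- HiDAC reductions, and any alvocidib reduction to level -1 (protocol Table 3, footnote b), concern agents inside the definition and would still be counted.

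**The case against.** The strongest reply is that the intent is not in real doubt. One line is wrong, while the synopsis, all three objectives and Section 6 are right. SAP Section 4 calls the protocol a companion document, and protocol 4.3.2 lists daunorubicin under a study-drug heading. A programmer who finds no mitoxantrone data would probably include daunorubicin. This stands as to the likely outcome, and it limits the weight of the point. It does not make the definition right. The protocol is also not uniform: 9.1 calls alvocidib the investigational study drug, while 9.3 uses study drugs for the whole regimen.

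A reader might infer more than the documents support:

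- *That the dose-change tables certainly miss daunorubicin.* Not shown. If action taken is recorded once for the regimen, they would include it.
- *That a daunorubicin cut would appear in no table.* Not established. SAP 7.7 also summarises reasons for departing from the protocol's dosing schedules, and that sentence does not rest on the defined term. A cut required by 4.4.4 may not be classed as noncompliance, so this is only a partial safeguard.
- *That the biomarker model covers nobody.* Objective 3 names cytarabine and daunorubicin, and SAP 7.8.1 specifies a CR model on MCL-1 dependence with no ACM restriction.
- *That relatedness tables change.* Relatedness is the investigator's judgement, and nothing shows that this definition alters it.
- *That an endpoint is affected.* Exposure is not among the endpoints in SAP Table 1, and neither exposure nor dose-change tables appear in protocol 7.1 or 11.3.4.

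**Conclusion.** The definition is wrong as written and should be corrected. The firm consequence is confined to exposure: read literally, SAP 7.7 omits one of three induction agents, a planned 180 mg/m² per patient in Induction, or 270 mg/m² with protocol Reinduction. The three dose-change titles may also be incomplete, depending on eCRF design. The ACM wording in 7.9 is a slip that the SAP's own third objective largely answers.

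This rests on a literal reading of Section 3, on planned rather than delivered doses, and, for the end of the TEAE window, on drugs being given in the scheduled order. No number of affected patients can be given. The documents do not support a claim that the MTD, DLT assessment, safety population or baseline is compromised.

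**What to change.** In the SAP:

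1. Section 3: define study drug as alvocidib, cytarabine (including HiDAC) and daunorubicin.
2. Sections 7.7 and 7.10.2: report exposure and dose changes separately for each agent, so that the tables do not depend on a collective term.
3. Section 7.9: replace ACM with alvocidib plus 7+3 (ACD).
4. Remove the CM abbreviation and correct the TPI-ALV-201 footers.

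The wording changes cost almost nothing and need no protocol amendment, patients or visits. Reporting by agent adds some table programming. For dose changes it also requires that the eCRF records action taken by agent. If it does not, the SAP should say that those tables refer to the regimen as a whole.

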11.3.2 Efficacy Analyses

Objective response to treatment will be determined using the remission definitions detailed in the 2017 European LeukemiaNet Recommendations in AML [10] after Induction/Reinduction (for those patients not achieving a CR after Cycle 1) (see [Appendix E](#)).

- CR_{MRD-} = CR without MRD
- CR = Complete Remission (including patients with morphologic CR who are MRD+ and cytogenetic and/or molecular marker positive)
- CR_i = CR with incomplete hematologic recovery
- MLFS = Morphologic leukemia-free state
- PR = Partial Remission
- SD = Stable Disease
- PD = Progressive Disease

The numbers of overall complete remissions (patients with a best objective response of CR_{MRD}, CR, CR_i or MLFS), and overall remissions (patients with a best objective response of CR_{MRD}, CR, CR_i, MLFS or PR) will be summarized by observed rates and estimated 95% CIs. If there are sufficient numbers of patients achieving remissions for an analysis to be informative, logistic regression will be used to model the probability of achieving a remission as a function of the total alvocidib daily dose level (bolus dose amount + infusion dose amount) and biomarker prediction endpoints (eg, MRD).

Kaplan-Meier time-to-event analyses will be conducted on overall survival, relapse-free survival and duration of remission. Mortality (all causes) at 30 and 60 days will also be calculated. Cox proportional hazards models will be fit to these time-to-event endpoints with the total alvocidib daily dose level (bolus dose amount + infusion dose amount) and biomarker prediction endpoints (eg, MRD) serving as independent variables in the model.

Additional exploratory analyses may be performed to assist the sponsor in planning future studies.

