APPENDIX E – RESPONSE CRITERIA (2017 EUROPEAN LEUKEMIANET RECOMMENDATIONS)

Category	Definition	Comment
Response		
• CR without minimal residual disease (CR _{MRD})	If studied pre-treatment, CR with negativity for a genetic marker by real-time quantitative polymerase chain reaction (RT-qPCR), or CR with negativity by multi-color flow cytometry	Sensitivities vary by marker tested, and by method used; therefore, test used and sensitivity of the assay should be reported; analyses should be done in experienced laboratories (centralized diagnostics)
• Complete remission (CR)	Bone marrow blasts <5%; absence of circulating blasts and blasts with Auer rods; absence of extramedullary disease; absolute neutrophil count $\geq 1.0 \times 10^9/L$ (1,000/ μ L); platelet count $\geq 100 \times 10^9/L$ (100,000/ μ L)	MRD positive or unknown*
• CR with incomplete hematologic recovery (CR _i)	All CR criteria except for residual neutropenia [$<1.0 \times 10^9/L$ (1,000/ μ L)] or thrombocytopenia [$<100 \times 10^9/L$ (100,000/ μ L)]	
• Morphologic leukemia-free state (MLFS)	Bone marrow blasts <5%; absence of blasts with Auer rods; absence of extramedullary disease; no hematologic recovery required	Marrow should not merely be “aplastic”; at least 200 cells should be enumerated or cellularity should be at least 10%
• Partial remission (PR)	All hematologic criteria of CR; decrease of bone marrow blast percentage to 5% to 25%; and decrease of pretreatment bone marrow blast percentage by at least 50%	Especially important in the context of phase 1-2 clinical trials

*Including patients with morphologic CR who are MRD+ and cytogenetic and/or molecular marker positive.

2017 EUROPEAN LEUKEMIANET RECOMMENDATIONS (Cont)

Category	Definition	Comment
Treatment failure		
• Primary refractory disease	No CR or CR _i after 2 courses of intensive induction treatment; excluding patients with death in aplasia or death due to indeterminate cause	Regimens containing higher doses of cytarabine (see Table 8) are generally considered as the best option for patients not responding to a first cycle of 7+3; the likelihood of responding to such regimens is lower after failure of a first
• Death in aplasia	Deaths occurring ≥ 7 days following completion of initial treatment while cytopenic; with an aplastic or hypoplastic bone marrow obtained within 7 days of death, without evidence of persistent leukemia	

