30- and 60-day survival, adverse events, time to neutrophil recovery, time to platelet recovery, prevalence of tumor lysis syndrome, clinical laboratory parameters, vital signs

Statistical Methods:

Descriptive statistics (including 95% confidence intervals) within and across alvocidib dose levels

2. Abbreviations

Standard abbreviations (e.g., AML = acute myeloid leukemia and mg = milligrams) are omitted intentionally.

AE Adverse Event

AML Acute Myeloid Leukemia
ANC Absolute Neutrophil Count

ATC Anatomical and Therapeutic Class

AUC Area Under Curve

BM Bone Marrow

BSA Body Surface Area
Cl Confidence Interval

CM Ara-C (Cytarabine) and Mitoxantrone

CMH Cochran-Mantel-Haenszel (test)

CR Complete Remission

CRi Complete Remission with Incomplete Blood Count Recovery

CTCAE Common Terminology Criteria for Adverse Events

DDE Drug Dictionary Enhanced

DLT Dose-Limiting Toxicity

DSMB (Independent) Data Safety Monitoring Board

ECOG Eastern Cooperative Oncology Group (performance status)

ELN European LeukemiaNet

HiDAC High-Dose Cytarabine

HR Hazards Ratio

ITT Intent-to-Treat (patient population)

IWG International Working Group

KM Kaplan-Meier (survivor function estimate)

LR Logistic Regression

MedDRA Medical Dictionary for Regulatory Activities

MRD- Minimal Residual Disease Negative

MTD Maximum Tolerated Dose

OS Overall Survival

PBSC Peripheral Blood Stem Cells
PFS Progression-Free Survival

PH Proportional Hazards (model)

PR Partial Remission

PT (MedDRA) Preferred Term

RFS Relapse-Free Survival

ROC Receiver Operating Characteristic (curve)

SAE Serious Adverse Event SAP Statistical Analysis Plan

SCT Stem Cell Transplant/Transplantation

SMQ Standardized MedDRA Query

SOC (MedDRA) System Organ Class

TEAE Treatment Emergent Adverse Event

TLS Tumor Lysis Syndrome

WHO World Health Organization

3. Definitions

Standard statistical terminology (e.g., type-1 error rate and significance level) is omitted intentionally. Efficacy endpoints are defined in Section 4.1 below (see Table 1).

Baseline Value: last measured value prior to the first dose of study drug

Combined CR: response assessment of CR or CRi

Combined Remission: response assessment of CR, CRi or PR

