4.1. Study Endpoints

Statistical analysis and/or summarization is planned for the following study endpoints. Complete details on how endpoints are calculated and compared across treatment arms are presented in the subsections below. A key to abbreviated terms appears in Section 2.

Table 1. Study Endpoints

Primary Efficacy Endpoint

 CR Rate: percentage of patients who achieve a CR as assessed by the investigator following treatment with alvocidib

Secondary Efficacy Endpoints (not listed in order of importance)

- CR_{MRD}
 Rate: percentage of patients who achieve a CR and test negative for minimal residual disease (MRD) using standardized techniques such as multiparametric flow cytometry or next generation sequencing
- Combined CR Rate: percentage of patients achieving a combined CR (CR or CRi) following treatment with alvocidib
- Combined Remission Rate: percentage of patients achieving a combined remission (CR, CRi or PR) following treatment with alvocidib
- Overall Survival: time from the date of first dose (Day 1) until death from any cause
- Progression-Free Survival: time from the date of first dose (Day 1) until (a) treatment failure, (b) relapse after combined remission (CR, CRi or PR), or (c) death from any cause, whichever occurs first
- Relapse-Free Survival Following CR (defined only for patients who achieve a CR during the study): time from the date of CR (Day 1) until (a) relapse after CR, or (b) death from any cause, whichever occurs first

Table 1. Study Endpoints

- Relapse-Free Survival Following Combined CR (defined only for patients who achieve a combined CR during the study): time from the earliest date of combined CR (Day 1) until (a) relapse after combined CR, or (b) death from any cause, whichever occurs first
- Relapse-Free Survival Following Combined Remission (defined only for patients who achieve a combined remission during the study): time from the earliest date of combined remission (Day 1) until (a) relapse after combined remission, or (b) death from any cause, whichever occurs first
- CR Duration (defined only for patients who achieve a CR during the study):
 time from the date of CR (Day 1) until relapse after CR
- Combined CR Duration (defined only for patients who achieve a combined CR during the study): time from the earliest date of combined CR (Day 1) until relapse after combined CR

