7.3. Visit Windows

Visit windows are not relevant for analyzing efficacy endpoints since these endpoints are either binary outcomes over the entire study period (e.g., CR rate) or measured on a continuous time scale (e.g., OS and PFS). Some safety assessments are summarized over time and within-cycle visit windows will be used (e.g., clinical laboratory parameters; see section 7.10.4).

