7.8.1. Remission Rates

The primary efficacy endpoint is CR rate as assessed by the investigator following treatment with alvocidib. Patients who, for any reason, do not supply bone marrow for response assessment are counted among those not achieving remission.

Summary statistics will include the number and percentage of patients rated as not achieving CR due to not providing a bone marrow biopsy/aspirate, proportion of patients who achieve a CR and exact 95% CI estimated without stratification. Between—treatment-arm statistics will include the Mantel-Haenszel odds ratio and 95% CI estimated with stratification.

A standard logistic regression (LR) model will be estimated relating the probability of achieving CR as a function of baseline MCL-1 dependence. Results will be presented graphically as follows. Patients will be divided into groups according to which range of values their baseline MCL-1 dependence falls:

$$(0\%-\leq d_1), (d_1-\leq d_2), (d_2-\leq d_3), \dots, (d_8-\leq d_9), (d_9-100\%)$$

where $d_1,...,d_9$ are deciles for baseline MCL-1 dependence regardless of treatment arm. Empirical CR rates will be calculated for patients within each range and plotted alongside CR probabilities estimated from the LR model.

Other remission rates (e.g., combined CR rate and combined remission rate) will be summarized similar to CR rate.

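### The SAP drops MLFS from the protocol's two remission rates without saying so, has no valid relapse criterion after PR, and can date a PFS failure at a Day 14 marrow that did not show failure

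*SAP*

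**What the plan says.** **Remission rates.** Protocol 11.3.2, like the Study Summary, defines overall complete remission as a best response of CR without MRD, CR, CRi or MLFS. Overall remission adds PR. Both are to be reported with intervals: the sentence ends "MLFS or PR) will be summarized by observed rates and estimated 95% CIs". SAP Section 3 has "Combined CR: response assessment of CR or CRi", and SAP Table 1 defines the wider rate as the "percentage of patients achieving a combined remission (CR, CRi or PR) following treatment with alvocidib". SAP 7.8.1 adds "Other remission rates (e.g., combined CR rate and combined remission rate) will be summarized similar to CR rate", naming the same two. The planned tables in SAP Table 3 list only these. MLFS is in none of the SAP's definitions, endpoints or abbreviations.

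**Treatment failure.** SAP Section 3 defines it as "failing to achieve a CR, CRi or PR following induction therapy", and SAP 7.8.2 makes it a PFS event.

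**Relapse.** PFS, RFS following combined remission and combined remission duration all use relapse after a remission that may be a PR. SAP Section 4 leaves relapse criteria to the protocol, and SAP Section 7 takes the AML relapse date from the clinical database. Protocol Appendix E defines hematologic relapse only after CR without MRD, CR or CRi, and molecular relapse only after CR without MRD.

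**Failure date.** SAP 7.8.2 uses the first marrow taken after the initial induction course, whether or not reinduction follows, unless reinduction brings a combined remission. A patient who misses the first response assessment and never remits instead gets that assessment's scheduled date. Protocol 5.2.5 schedules a marrow at Day 14 (±3). Under Protocol 4.1, patients without residual leukemia then wait for response assessment at hematologic recovery or Day 50 (±3), whichever is earlier.

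**The concern.** Two remission rates that the protocol undertakes to report have no definition or table in the SAP. Narrower rates with similar names take their place without comment. A patient whose best response is MLFS counts as a complete-remission responder under Protocol 11.3.2 and as an induction failure under the SAP.

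Two derivations are also left open. A programmer has no criterion by which to accept or reject a recorded relapse in a patient whose best response was PR. And a patient without residual leukemia at Day 14 who later fails to remit can be given a PFS event on the date of a marrow that did not show failure. At stake are the composite rates, the early part of the PFS curve, and RFS and duration following combined remission.

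**Working it through.** **1. Composites side by side**

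| Rate | Protocol 11.3.2 | SAP Section 3 and Table 1 | Missing from SAP |
|---|---|---|---|
| Complete remission composite | CR without MRD, CR, CRi, MLFS | CR, CRi | MLFS |
| Remission composite | as above plus PR | CR, CRi, PR | MLFS |

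CR without MRD is not lost: it is a subset of CR and has its own rate in SAP Table 1. Only MLFS drops out.

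Each MLFS-only patient shifts a composite by 100/N points:
- MTD level of 26 (6 + 20, Protocol 11.2): 100/26 = 3.8
- SAP Appendix 2 sample table, all patients: 100/22 = 4.5
- same table, 30/60 level: 100/13 = 7.7
- a level of 3: 100/3 = 33.3

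For scale, assume 13 of 22 patients reach CR or CRi (the documents give no expected rate):
- SAP rate: 59.1% (exact 95% CI 36.4 to 79.3)
- protocol rate with 1 MLFS-only patient: 63.6% (40.7 to 82.8)
- protocol rate with 4 such patients: 77.3% (54.6 to 92.2)

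No MLFS count is given. SAP 7.3 says of the efficacy endpoints that "these endpoints are either binary outcomes over the entire study period (e.g., CR rate"), so an MLFS patient whose counts later recover leaves the category. The number may be zero.

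**2. Relapse after PR**

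Appendix E's PR requires, among other things, a "decrease of bone marrow blast percentage to 5% to 25" percent. Its hematologic relapse criterion is marrow blasts of at least 5%, blasts reappearing in blood, or extramedullary disease. Every marrow blast value in the PR range already meets the first of these, so the CR criterion cannot be borrowed for PR. Appendix E also defines progressive disease, but the SAP does not list it as a PFS event. The CR and CR/CRi variants are unaffected.

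**3. Failure date for a patient without residual leukemia at Day 14 who never remits**

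- Literal SAP date: Day 14, or 12/365.25 × 14 = 0.46 months.
- Date at the latest nominal response assessment: Day 50, or 12/365.25 × 50 = 1.64 months.
- Nominal difference: 50 − 14 = 36 days, or 1.18 months.
- Shortest with both windows: 47 − 17 = 30 days.
- Longest: cytarabine runs as a continuous infusion through Day 11 (Protocol 4.3.2), so a marrow after induction is not expected before about Day 12. 53 − 12 = 41 days.
- If counts recover before Day 50, the assessment is earlier and the difference smaller.

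Six months is 6 × 365.25/12 = 182.6 days. Both candidate dates precede it, so the patient counts as failed at every listed milestone (6, 12 and 18 months) either way. Only early PFS times move, and possibly the lower quartile at a small dose level.

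**The case against.** Protocol Section 11 calls itself a brief overview and leaves detail to the SAP. Protocol 7.2 says a formal efficacy analysis is not appropriate, and supporting efficacy data are listed by patient. This limits the consequence. It does not explain why two named rates disappear without a declared departure.

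The MLFS failure rule contradicts no protocol endpoint, because PFS appears only in the SAP. Appendix E's primary refractory category, no CR or CRi "after 2 courses of intensive induction treatment; excluding patients with death in aplasia or death due to indeterminate cause", does not count MLFS as success either. That stands. Protocol 6.2, however, groups MLFS with the responses that keep a patient from being considered for removal for lack of response, so its status needs stating.

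A reader might infer that a PR patient has no recordable relapse event at all. The documents do not support that: SAP Section 7 takes the relapse date from the database. What is missing is a valid criterion for recording it.

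On the failure date, the author may have meant the response-assessment marrow. The protocol calls Day 14 a disease assessment and places both marrows under Induction. The literal text points to Day 14, and the reference to a second induction fits the marrow that decides reinduction, but the other reading is plausible.

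A reader might also infer that attending the assessment and failing always gives an earlier PFS event than missing it. That depends on which rule in 7.8.2 prevails. A patient with no response marrow is counted as not in remission, and PFS takes the earliest event, so the failure rule could date that patient at Day 14 too.

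**Conclusion.** The MLFS discrepancy is firm: both protocol composites include it, neither SAP composite does, and no departure is declared. Its size is 100/N points per MLFS-only patient, possibly zero in total, and the CR rate does not change.

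The PR gap is minor. It is a missing criterion confined to PFS, RFS following combined remission and combined remission duration.

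The failure-date point rests on a literal reading of SAP 7.8.2 and on the marrow schedule being followed. On that reading PFS failure is about 36 nominal days early (roughly 30 to 41 with windows) for patients without residual leukemia at Day 14 who never remit. Dating at Day 14 is acceptable for patients whose Day 14 marrow was positive, including those reinduced.

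The documents do not say how many such failures to expect, so whether the lower PFS quartile actually moves cannot be established. These points should be settled before analysis, but they do not threaten the study's safety objective or its CR rate.

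**What to change.** 1. **Remission rates.** Add the two Protocol 11.3.2 composites, with MLFS, to SAP Section 3, Table 1, 7.8.1 and Table 3. Keep CR/CRi and CR/CRi/PR as additional summaries. State whether MLFS is a failure for PFS. If it is not, also state the event that ends it, because Appendix E's relapse definition does not cover MLFS.

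2. **PR.** Limit RFS and remission duration to the CR and CR/CRi variants already planned. For PFS, state the event that ends a PR and how its date is recorded.

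3. **Failure date.** In SAP 7.8.2, take patients whose Day 14 marrow does not meet Protocol 4.1's residual-leukemia definition (more than 5% blasts plus more than 10% cellularity). Date failure at the first later marrow, scheduled or unscheduled, that documents persistent leukemia. Otherwise date it at the recovery or Day 50 response assessment that documents non-remission. Phrasing it this way covers mixed marrows, which Protocol 4.1 puts in neither group, and does not post-date a failure already seen on a discretionary marrow. Keep the scheduled-date rule for a missed assessment and say that it prevails. Leave Day 14-positive patients as they are.

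**Cost.** Items 1 and 3 need only SAP wording and derivations. Item 2 needs a definition and a way to record loss of PR, because long-term follow-up (Protocol 5.6.2) asks only about death, transplant, relapse or continued remission, by phone or from records. The downside is that PFS becomes slightly longer for some induction failures.
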